13 ETHICAL AND REGULATORY CONSIDERATIONS	
14. DISSEMINATION POLICY	
15. REFERENCES	
16. APPENDICIES	

ii. LIST OF ABBREVIATIONS

BAP1 BRCA-associated protein 1

CA Competent Authority

CAG Confidentiality Advisory Group

CI Chief Investigator
CRF Case Report Form

FEV1 Forced expiratory volume in 1 second

FISH fluorescence in situ hybridisation

GCP Good Clinical Practice

GMP Good Manufacturing Practice

ICF Informed Consent Form

ICH International Conference on Harmonisation of technical

requirements for registration of pharmaceuticals for human

use.

IHC Immunohistochemical

ISF Investigator Site File (This forms part of the TMF)

ISRCTN International Standard Randomised Controlled Trials

Number

MDT Multi-Disciplinary Team

MTAP methylthioadenosine phosphorylase

NHS R&D National Health Service Research & Development

PI Principal Investigator

PIC Participant Identification Centre
PIS Participant Information Sheet

PET-CT Positron Emission Tomography CT

PPI Patient and Public Involvement

PM Pleural Mesothelioma
QA Quality Assurance
QC Quality Control

REC Research Ethics Committee
SDV Source Data Verification

SOP Standard Operating Procedure

SSI Site Specific Information

TMF Trial Master File

TMG Trial Management Group
TSC Trial Steering Committee

iii. TRIAL SUMMARY

Trial Title	Reducing Repeat Pleural Biopsies In Suspected Cancer – a study of the TARGET trial cohort			
Internal ref. no. (or short title)	REPLICA			
Trial Design	additional diagnostic tests in no could increase the diagnosis ramalignancy. Standard pathway	A UK based multicentre study to evaluate whether performing additional diagnostic tests in non-diagnostic pleural biopsies could increase the diagnosis rate in suspected pleural malignancy. Standard pathway vs proposed (involving additional diagnostic tests) pathway		
Trial Participants	A study of the 59 participants who enrolled in the RCT TARGET study at 8 UK sites between September 2015 and September 2018. Inclusion criteria included suspicious pleural thickening on CT scan, non-diagnostic pleural biopsy and MDT decision to perform further CT-guided biopsy to pursue a diagnosis.			
Planned Sample Size	59 participants were enrolled in TARGET. Total sample size is 118, as each participant provides matched data for both standard and proposed pathways. 129 biopsy samples available in total.			
Follow up duration	12 months (already completed as part of TARGET trial)			
Planned Trial Period	12-18 months total			

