	Objectives	Outcome Measures		
Primary	Identify patients for whom additional pathological testing would have yielded a definitive diagnosis on baseline biopsy, avoiding the need for further invasive tests	Identification of malignancy on biopsy (binary; diagnostic vs non-diagnostic) via: i) histopathological confirmation on standard testing or histopathological features of PM with demonstrated BAP1, p16 or MTAP deletion or iii) Multi-disciplinary Team (MDT) diagnosis		
Secondary	i) Investigate whether additional pathological testing would have shortened the overall time to diagnosis and ii) Investigate whether additional testing would have reduced costs	i) Total number of biopsies required ii) Time to diagnosis iii) Stage at diagnosis iv) Number of MDT discussions required v) Biopsy-associated costs vi) Biopsy-related adverse events		

in whom additional testing would have provided a definitive diagnosis

iv. FUNDING AND SUPPORT IN KIND

FUNDER(S) (Names and contact details of ALL organisations providing funding and/or support in kind for this trial)	FINANCIAL AND NON FINANCIALSUPPORT GIVEN
Southmead Hospital Charity [name] [contact]	Research grant
NBT NHS Trust	Salaries for [name], [name], [name], [name]
NIHR	Salary for [name]
University of Bristol	Salary for [name]
University of West of England	Salary for [name]

v. ROLE OF TRIAL SPONSOR AND FUNDER

The Sponsor and Funders have no role or remit in the study design, conduct, data analysis and interpretation, manuscript writing or dissemination of results.

vi. ROLES AND RESPONSIBILITIES OF TRIAL MANAGEMENT COMMITEES/GROUPS & INDIVIDUALS

Study management group:

Responsible for oversight of the study. It will monitor trial progress, ensure all practical details of the trial are progressing well and feed back to the sponsor. The study management group will be chaired by the CI and will include all members of the named research team. It will meet 4 times during the study period.

Patient and Public Involvement group:

IRAS ID 329574

This will involve a specialist nurse and trial co-ordinator communicating details of the trial progress to a group of mesothelioma patients and carers as the study progresses.

Study delivery group:

This involves the people responsible for retrieving histological samples and performing and reporting the pathological tests. They will ensure accuracy and reproducibility of the tests, and updating the investigators on progress.

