1 BACKGROUND

Plain English Summary:

Pleural mesothelioma (PM) is a cancer that affects the outside lining of the lung, caused by asbestos exposure. The UK has the highest rate of PM in the world, but despite recent treatment advances, average life expectancy remains under a year from diagnosis. Prompt diagnosis is therefore vital.

People with suspected PM usually require a biopsy of the lung lining to confirm the diagnosis, guide treatment and assist with compensation claims. However, some people need multiple biopsies which increases the risk of biopsy-related complications and prolongs the diagnostic process, causing additional stress and anxiety.

Some people with mesothelioma can deteriorate rapidly. A prolonged time to diagnosis could mean the time window in which someone is sufficiently strong to tolerate life-prolonging treatment is missed.

We believe doing additional tests on initial biopsies will increase the chance of diagnosing PM, avoiding repeat biopsies. This will shorten the period of anxious uncertainty and allow patients to start anti-cancer treatment sooner, improving their chances of survival. Reducing the number of biopsies will eliminate the risks associated with multiple procedures and free up space for other patients with suspected cancer, improving their diagnostic pathway as well.

The extra tests – while not genetic tests – look for markers of genetic changes that happen in PM. Genes are the building blocks in every cell of our bodies that make up who we are and how our bodies behave. Some genes work to stop tumours appearing and, if they do appear, stop them growing. PM tumours can stop these protective genes working or make them disappear, which allows the tumour to grow and spread inside the body. The markers affected in PM are called BAP1, p16 and MTAP and we can test biopsy samples for these. If all three have disappeared, then we can make a diagnosis of mesothelioma.

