We previously conducted a study of people with suspected PM who required further biopsies as their first biopsy did not diagnose the condition. All patients consented to be in this trial and an application is underway for approval to perform additional tests on the trial samples. We want to re-test their original and follow-up biopsy samples for BAP1, p16 and MTAP to see whether this would have made the diagnosis sooner and removed the need for further biopsies. We will investigate how many biopsies could have been avoided, how much time would have been saved, and what cost-savings this would have offered the NHS.

BAP1, p16 and MTAP are not routinely used in clinical practice and are not available at many hospitals, despite being relatively inexpensive. BAP1 is already available in NBT and MTAP is undergoing set up. The cost of setting up MTAP is between £150-£400.

We hope our research will show how useful these tests are and how much benefit they offer to patients and NHS services, so they can be used more widely in routine care. Ultimately, we expect our research to be included in national guidelines and change clinical practice across the UK and worldwide.

Scientific summary:

Pleural Mesothelioma (PM) is a primary incurable malignancy of the pleural surface, associated with prior asbestos exposure. Median survival is 9-12 months. Chemotherapy offers marginal therapeutic benefit, but combination immunotherapy has shown promise in recent phase III trials. [1, 2]

Diagnosing PM can be challenging. Radiology supports diagnosis but pathological diagnosis is the gold standard. Some patients present with pleural effusions but pleural fluid sensitivity for PM is low. Pleural biopsy has higher diagnostic sensitivity, but this drops with smaller samples and certain histological subtypes [3]. As a result, some patients undergo multiple investigations, with increased risk of complications and delays to treatment initiation.

Our research unit has previously studied potential approaches to enhance the PM diagnostic process. The multi-centre randomised TARGET trial studied whether Positron Emission Tomography CT (PET-CT) directed biopsy improved the diagnostic yield of biopsies in people with previous non-diagnostic biopsies [4]. PET-CT did not improve diagnostic rates and some repeat biopsies were also non-diagnostic, necessitating further invasive procedures.

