6 PARTICIPANT ELIGIBILITY CRITERIA

IRAS ID 329574

All patients recruited for the TARGET study will be included, provided they have sufficient stored biopsy material to undertake the required additional tests.

TARGET eligibility required all of the following to apply:

- Pleural thickening on CT suspicious for pleural malignancy
- Have had any form of pleural biopsy in the last 12 months (either by thoracoscopy or under radiological guidance) which was non-diagnostic for cancer
- Lung Cancer/mesothelioma MDT decision to perform further CT-guided biopsy to pursue a diagnosis

Participants were ineligible for TARGET if ANY of the following applied:

- Unsuitable for a CT guided biopsy (inability to co-operate, lie still for the duration of the biopsy, uncorrectable coagulopathy, inability to tolerate a pneumothorax, severe underlying lung disease [patients with an FEV1 < 35% assessed using simple spirometry])
- Unable to give written informed consent
- Pregnancy or lactation
- Age<18 years
 Pleural thickening not amenable to a radiologically guided biopsy
- Talc pleurodesis in the previous 6 months

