7.3 Data extraction

Baseline clinical information and follow up data from visits at 3, 6 and 12 months will be extracted from the trial database. Where this data is unavailable, it will be sought from medical records. Variables include:

- Baseline demographic data
- Asbestos exposure history
- Relevant medical background
- Biopsy dates and results
- Biopsy method
- Number of biopsies required for diagnosis
- Biopsy-related adverse events
- Histological diagnosis
- Whether diagnosis was tissue based or clinico-pathological.
- Time to diagnosis (from enrolment)
- Stage at diagnosis
- Number of MDT discussions

- MDT outcomes including ultimate MDT diagnosis and date of diagnosis
- Radiological images and reports used during diagnostic period
- Anti-cancer treatment received
- Healthcare utilisation
- Overall survival

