10 STATISTICS AND DATA ANALYSIS

The independent variable is the availability of BAP1, p16 FISH and MTAP testing (binary; available *vs* not available). The primary outcome is identification of malignancy on biopsy (binary; diagnostic *vs* non-diagnostic), with diagnosis defined as i) histopathological confirmation on standard testing or ii) histopathological features of PM with demonstrated BAP1, p16 or MTAP deletion or iii) Multi-disciplinary Team (MDT) diagnosis. It is assumed that confirmation of a malignant diagnosis stops the diagnostic pathway with no additional biopsies required. Any subsequent biopsies for these participants will not be included in the analysis, preventing double-counting. Secondary outcomes include total number of biopsies required, time to diagnosis, stage at diagnosis, number of MDT discussions, biopsy-associated costs, biopsy-related adverse events and survival. Potential confounding variables include age, sex, biopsy method and tumour histology and these will be adjusted for, when possible, in the analysis.

Outcome measures will be tabulated for standard and proposed pathways and compared using descriptive statistics (including the McNemar test). Univariable and multivariable logistic regression will look for an association between the availability of these tests and likelihood of a diagnostic biopsy. The relationship between secondary outcomes and availability of the tests will be evaluated using adjusted and unadjusted regression analyses and time to event analysis (cox proportional hazard model).

Sample Size:

Total number of patients: 59

Total histological samples for analysis: 129 (all participants had multiple biopsies)

REPLICA

IRAS ID 329574

Each participant will be assessed as a case (proposed pathway) and as an internal control (standard pathway) generating two groups of 59 = 118 records for inclusion in the study

Sample size is determined by the number recruited to the TARGET study which demonstrated diagnostic sensitivity (without these additional tests) of 30%. A sample size of 118 (59 in each arm) will allow detection of an increased diagnostic rate of 60% with 95% confidence intervals of +/- 8.8% (based on BAP1 loss prevalence of 60%).

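### A single Cox hazard ratio does not measure the time saved to diagnosis when each participant supplies two linked records, and death before diagnosis is a competing event the plan does not address

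*Protocol*

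**What the plan says.** The trial summary sets the secondary objective of finding out whether "additional pathological testing would have shortened the overall time to diagnosis", and lists time to diagnosis among the outcome measures. Section 10 analyses secondary outcomes by adjusted and unadjusted regression and by "time to event analysis (cox proportional hazard model". That is the only time-to-event method in the protocol. Section 10 does not say what happens to a participant who dies before any diagnosis.

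Sections 4 and 10 make each participant both case and internal control, so 59 people give 118 records. Section 7.3 extracts "Time to diagnosis (from enrolment"), along with the date of the final MDT diagnosis and overall survival. The trial summary gives follow-up as "12 months (already completed as part of TARGET trial").

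On mortality, the scientific summary in Section 1 says "Median survival is 9-12 months", for pleural mesothelioma. The plain English summary says "average life expectancy remains under a year from diagnosis". The cost of delay is part of the rationale: "A prolonged time to diagnosis could mean the time window in which someone is sufficiently strong to tolerate life-prolonging treatment is missed".

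**The concern.** The objective is a question about an amount of time, and the design answers it person by person: the same individual has a diagnosis date under each pathway. A hazard ratio does not return that amount. It also fits this data structure poorly, because the added tests do not speed up diagnosis steadily. They move some people to one early date and leave the others exactly where they were.

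A Cox model has one event type, so by default someone who dies undiagnosed is censored. That is acceptable if the result is read as a cause-specific hazard ratio. It is not acceptable if event curves or median times from the same data are read as the proportion or timing of patients actually diagnosed.

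At stake are a headline ratio that moves with mortality while the tests stay the same, and a result in which people who never reached a diagnosis are not counted as such.

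**Working it through.** The plan gives no figure for time to diagnosis or for deaths before diagnosis, so there is none to reproduce. The precision figures in Section 10 concern the diagnostic rate and do not bear on this point.

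**Step 1. Direction, without assumptions about rates.** Let T0 and T1 be one person's diagnosis times under the standard and proposed pathways, and D the death time common to both. Added tests can only bring diagnosis forward, so T1 ≤ T0. Whenever D < T1, also D < T0. Death before diagnosis therefore cannot be rarer in the standard pathway.

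**Step 2. Non-proportional hazards.** For a person converted at the index biopsy, T1 is that early date; for anyone not converted, T1 = T0. The proposed pathway thus has a spike of diagnoses at the start. If conversion is unrelated to later diagnosis time, the hazards afterwards are equal. A Cox fit averages a very large early ratio with a ratio near 1 later. Deaths remove later events, where the ratio is near 1, so they push the average up.

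**Step 3. Size of the shift in the hazard ratio (simulation).** Assumptions, none given in the protocol unless noted:
- 40% converted at the index biopsy
- 30% diagnosed at a repeat biopsy at 1.5 months (30% is the standard sensitivity in Section 10)
- the rest diagnosed later, with a median of 3, 6 or 12 months
- enrolment at 1 month, clock from the index biopsy, 12-month cap
- exponential survival from enrolment with a median of 9 or 12 months

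Results:
- Hazard ratio 1.61–1.86 without deaths and 1.69–2.15 with them. The ranges overlap because each spans the three later-diagnosis medians. End to end the shift is 1.69 − 1.61 = 0.08 and 2.15 − 1.86 = 0.29.
- Undiagnosed deaths about 10–20 of 59 (standard) and 6–11 (proposed).
- If 30% of the cohort are never diagnosed and do not die in follow-up, standard-pathway undiagnosed deaths fall to about 6–14, and the hazard ratio still moves, for example from 1.40 to 1.55. If later diagnosis is also fast (median 1 month), deaths fall to about 3–4.

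As a contrast, with a constant true hazard ratio of 2.0 and deaths censored, a Cox fit returned 2.02 and 2.01. Censoring deaths does not by itself bias the cause-specific ratio. The dependence on mortality comes from the non-proportionality in step 2.

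**Step 4. How many might die undiagnosed.** Take constant hazards: death d = ln 2/S with S = 9 or 12 months applied from enrolment (an assumption), and diagnosis l = ln 2/m with m assumed. Over 12 months:
- died undiagnosed = d/(l+d) × (1 − exp(−12(l+d)))
- cumulative incidence of diagnosis = l/(l+d) × (1 − exp(−12(l+d)))
- 1 − Kaplan-Meier with deaths censored = 1 − exp(−12l)

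Example, m = 2 and S = 9: l = 0.347, d = 0.077, l+d = 0.424. Died undiagnosed = 0.182 × 0.994 = 0.181, or 10.7 of 59. Cumulative incidence is 0.813 against a 1 − Kaplan-Meier of 0.984, a gap of 17 points.

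| m (months) | Died undiagnosed, of 59 (S = 12 / 9) | 1 − KM | Cumulative incidence (S = 12 / 9) | Gap, points |
|---|---|---|---|---|
| 0.5 | 2.4 / 3.1 | 1.000 | 0.960 / 0.947 | 4 / 5 |
| 1 | 4.5 / 5.9 | 1.000 | 0.923 / 0.900 | 8 / 10 |
| 2 | 8.4 / 10.7 | 0.984 | 0.850 / 0.813 | 13 / 17 |
| 3 | 11.4 / 14.4 | 0.938 | 0.775 / 0.731 | 16 / 21 |
| 6 | 17.2 / 21.3 | 0.750 | 0.583 / 0.540 | 17 / 21 |

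All-cause mortality at 12 months under the same S is 1 − exp(−12d) = 0.50 to 0.60 (29.5 to 35.6 of 59). That is a different quantity, because deaths after diagnosis do not compete with diagnosis.

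**The case against.** Much of the opposing case stands.

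- **The survival figure.** A reader might infer from 9–12 months that many participants would die undiagnosed. The documents do not support that. The figure is for mesothelioma, and the plain English summary counts life expectancy from diagnosis. The cohort was enrolled on "Pleural thickening on CT suspicious for pleural malignancy", so not all need have mesothelioma. An MDT diagnosis also counts as a diagnosis under Section 10. No number of undiagnosed deaths is given.
- **The analysis criticised.** The protocol does not say deaths are censored and plans no Kaplan-Meier proportion diagnosed. The gaps in the table arise only if curves or medians are reported that way. Detailed censoring rules may sit in an analysis plan that is not shown.
- **The method is not wrong.** Cox with deaths censored is a valid cause-specific analysis.
- **Hiding a harm.** A reader might infer that the plan conceals deaths without a diagnosis. It does not: survival is a listed outcome, and diagnostic status is compared separately by McNemar test and logistic regression. Death without diagnosis is simply not a named outcome.
- **The simulation's clock.** It starts at the index biopsy, whereas Section 7.3 counts from enrolment. Its figures illustrate the mechanism and do not forecast the result.
- **The alternative also depends on mortality.** Time undiagnosed stops at death, so time saved falls as mortality rises.

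Two things are left. Non-proportionality follows from the design the protocol states, whatever the death rate. And a within-person difference, although it too depends on mortality, is in units of time and answers the stated objective, with the deaths shown beside it.

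**Conclusion.** The point holds as a cheap improvement, not as an error that invalidates the plan. Naming a Cox model as the only time-to-event method leaves the objective without a direct measure, and the single ratio it yields averages over hazards that cannot be proportional here. Under the stated assumptions, the same test performance gives about 1.6–1.9 without deaths and up to about 2.2 with them.

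The excess, if any, of undiagnosed deaths lies in the standard pathway; this needs only a shared death date and diagnosis never being later with the added tests. Its frequency is an assumption throughout: roughly 2 to 20 of 59 for median diagnosis times of 0.5 to 6 months. Any overstatement of the proportion diagnosed, about 4 to 21 points over that range, is conditional on deaths being treated as ordinary censoring in reported curves or medians.

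**What to change.** In Section 10:

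1. Make the main measure for time to diagnosis the within-participant difference (standard minus proposed) in time alive and undiagnosed up to 12 months, with a confidence interval from resampling participants so that the two records of a person stay together. State the origin and the 12-month limit: Section 7.3 counts from enrolment, but the index biopsy comes earlier, so a diagnosis moved to that biopsy would fall before time zero.
2. Report for each pathway the 12-month cumulative incidence of diagnosis (Aalen-Johansen), with death without diagnosis as the competing event, and the number who died undiagnosed.
3. Keep the Cox hazard ratio as a secondary result, labelled cause-specific.

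The cost is a few sentences and a little analysis work. Dates of diagnosis and overall survival are already on the extraction list in Section 7.3. The downside is that a familiar single hazard ratio is no longer the headline for this outcome.

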Recent advances since TARGET have broadened the panel of tests available for PM biopsy samples. Homozygous deletion of the 9p21 locus is one of the most common genetic alterations in PM, affecting a cluster of tumour suppression genes that show diagnostic promise. These are BRCA-associated protein 1 (BAP1), p16 and methylthioadenosine phosphorylase (MTAP) [4, 5].

BAP1 is a tumour suppressor gene that is mutated in 40-60% of PM tumours, causing loss of BAP1 expression. A 2017 meta-analysis showed BAP1 loss had moderate diagnostic sensitivity (area under the curve of 0.72) with 100% specificity, making it an excellent 'rule-in' test for PM [6].

P16 deletion occurs in 80% of PM and is demonstrated using fluorescence in situ hybridisation (FISH). Diagnostic sensitivity of P16 FISH is 0.53, but 0.76 if combined with BAP1 testing [7].

FISH is not performed in all laboratories but immunohistochemical (IHC) staining is universally available. IHC expression of the protein product of the MTAP gene has been shown to be an accurate and reproducible surrogate marker for p16 FISH, with 78% sensitivity and 96% specificity for homozygous p16 deletion and is faster and cheaper to run [8]. When used in combination with BAP1, MTAP IHC has 100% specificity and 76.5% sensitivity for differentiating between malignant and benign mesothelial disease [6].

BAP1, p16 FISH and MTAP are used in some UK centres but are not universally available nor routinely recommended in current guidelines [9-11].

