On the assumption that the combination of BAP1 and MTAP will increase the diagnostic rate still higher, a sample size of 118 will allow detection of an increased diagnostic rate of 70% with 95% confidence intervals of +/- 8.2% and a diagnostic rate of 80% with 95% CI of 7.2%

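### The 30% comparator cannot apply to the baseline-biopsy objective, where standard testing scores 0 by eligibility; the wider Section 10 outcome is not reconciled with it, and the participant-level McNemar test can go only one way

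*Protocol*

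**What the plan says.** The primary objective in the Trial Summary is to "Identify patients for whom additional pathological testing would have yielded a definitive diagnosis on baseline biopsy", so that further invasive tests could have been avoided. Section 6 gives the TARGET entry conditions. One is "Have had any form of pleural biopsy in the last 12 months (either by thoracoscopy or under radiological guidance) which was non-diagnostic for cancer"; another is an MDT decision to biopsy again. Section 6 also limits REPLICA to participants with enough stored tissue.

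The outcome in Section 10 (and in the Trial Summary's outcome column) is wider than the objective. A diagnosis counts if it comes from standard histology, from features of pleural mesothelioma (PM) with loss of BAP1, p16 or MTAP, or from the MDT. Standard and proposed pathways are compared, and only biopsies taken after a malignant diagnosis are left out. The analysis names the McNemar test and logistic regression on test availability.

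On sample size, Section 10 says: "Sample size is determined by the number recruited to the TARGET study which demonstrated diagnostic sensitivity (without these additional tests) of 30" per cent. It counts each participant once per pathway, "generating two groups of 59 = 118 records for inclusion in the study", and states that this number "will allow detection of an increased diagnostic rate of 60% with 95% confidence intervals of +/- 8.8" per cent, based on a BAP1 loss prevalence of 60%. For BAP1 plus MTAP it adds "an increased diagnostic rate of 70% with 95% confidence intervals of +/- 8.2% and a diagnostic rate of 80% with 95% CI of 7.2" per cent. The Background says "BAP1 is a tumour suppressor gene that is mutated in 40-60% of PM tumours" and gives BAP1 plus MTAP a sensitivity of 76.5%.

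**The concern.** The sample-size text invites the reader to see the result as a rise from 30% to 60% or more. If the primary result is about the baseline biopsy, that contrast is not available, because every participant was selected for having a non-diagnostic result on it. A test against a comparator fixed at zero says little, since any handful of positive marker results will reject the null. If the result is instead about the whole pathway, the comparator is different and the question is no longer the one in the objective: a diagnosis reached only on a repeat biopsy has not spared that biopsy.

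The Rationale expects the findings to inform national guidelines. A small p-value or a large odds ratio could be read as evidence of a useful panel when it mostly reflects how the two pathways are defined.

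**Working it through.** **Step 1. Reproduce the stated precision.** The Wald half-width for one proportion is 1.96 × √(p(1 − p)/n).

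| Rate p | Printed | n = 118 | n = 59 |
|---|---|---|---|
| 60% | 8.8 | 1.96 × √(0.24/118) = 8.84 | 12.50 |
| 70% | 8.2 | 1.96 × √(0.21/118) = 8.27 | 11.69 |
| 80% | 7.2 | 1.96 × √(0.16/118) = 7.22 | 10.21 |

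The printed figures come from n = 118 (8.27 appears as 8.2, that is, truncated). They describe a single proportion with every patient counted twice. The diagnostic rate under the proposed pathway has at most 59 participants behind it, so the half-widths are 12.5, 11.7 and 10.2 points. The 30% does not enter the formula.

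**Step 2. Standard result on the baseline biopsy.** Section 6 required that biopsy to be non-diagnostic, so standard histology is unmet. It also required the MDT to be still seeking a diagnosis, so the MDT route is unmet at entry. The standard count is 0 for everyone, by selection. The 30% must describe something else. Section 10 does not say whether it refers to initial or repeat biopsies, or to patients or samples. It is called a sensitivity, whose denominator is people with the disease, yet it stands beside a diagnostic rate, whose denominator is everyone tested.

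**Step 3. Standard result on the pathway reading.** Repeat biopsies and MDT diagnoses count. The Background says that some repeat biopsies were also non-diagnostic, which implies that others were diagnostic, so the standard rate is above 0. The protocol does not say by how much at participant level. If it were 30%, that would be 0.30 × 59 = 17.7, about 18 participants.

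**Step 4. The McNemar test.** Let b be participants diagnosed only under the proposed pathway and c those diagnosed only under the standard one. The proposed pathway keeps every standard route and adds one, so c = 0 at participant level on both readings. The exact two-sided p-value is then 2 × 0.5^b:

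- b = 5: p = 0.0625
- b = 6: p = 0.031 (6/59 = 10.2%)
- b = 18, the nested rise from 30% to 60%: p = 7.6 × 10⁻⁶

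With 59 participants, the probability of b ≥ 6 is 0.55 at a true added yield of 10%, 0.89 at 15%, 0.986 at 20% and above 0.999 at 30%. Significance is close to assured at yields far below those planned for.

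**Step 5. Logistic regression on the baseline reading.** With 0/59 under standard testing, any positives under the proposed pathway separate the data. A trial fit of 0/59 against 35/59 did not converge (log odds ratio about 24, standard error about 19,000). There is no finite odds ratio to report.

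**Step 6. What can be estimated.** With c = 0 the paired difference (b − c)/n is simply b/n. For 18/59 (30.5%) the exact 95% CI is 19.2 to 43.9%; for 35/59 (59.3%) it is 45.7 to 71.9%.

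**Step 7. The target rates.** The 60% is the top of the protocol's 40–60% range for BAP1, and that range applies to PM tumours, not to a cohort with suspected malignancy. The 80% is tied to BAP1 plus MTAP, for which the Background gives a sensitivity of 76.5%; if marker yield alone is meant, 80% exceeds it.

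**The case against.** The best defence is that Section 10 describes a pathway comparison. Its outcome is not restricted to baseline, and repeat biopsies and MDT diagnoses score under the standard pathway. On that reading the comparator is not 0/59 and logistic regression can give a finite odds ratio. This stands. A reader might infer that the standard rate is 0/59 for the primary outcome as such, but the documents support that only for the baseline-biopsy objective. Nor is 59 a fixed denominator: the tissue requirement makes it a maximum. And if individual biopsies were the unit, c = 0 would not be guaranteed, because the two pathways would contribute different biopsies.

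A reader might also infer that the study was powered on a false 30% versus 60% contrast. It was not. The protocol claims precision, not power, and the 30% plays no part in the calculation. The cohort is already complete, so its size cannot change, and the McNemar test is listed among descriptive statistics.

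Finally, 76.5% is not a ceiling on the diagnostic rate. Section 3 adds p16 FISH where BAP1 and MTAP fail, and the outcome also counts standard histology and MDT diagnoses.

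These points narrow the finding but do not remove it. The pathway reading leaves the objective and the outcome in conflict, and the participant-level McNemar test remains one-directional under it.

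**Conclusion.** The point holds in this form. For the stated primary objective, the standard result is 0 by eligibility and the 30% cannot be its comparator. Section 10's wider outcome has a standard rate above 0, but the protocol does not say which of the two is primary or what the 30% measures. On both readings, with the participant as the unit, one discordant cell is zero by construction, and 6 re-diagnosed participants of 59 give p = 0.031. The odds ratio for test availability is not estimable on the baseline reading only. The printed precision is too narrow for 59 participants by about 3 to 4 points in half-width (8.8 against 12.5 at a rate of 60%, for example).

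The one-directional result assumes that both pathways use the same Section 10 definition and that the proposed pathway removes no standard route. The figures use n = 59; fewer evaluable participants would widen the intervals, while the threshold of 6 would not change. The documents do not give the share of the cohort with PM, so no expected yield is computed here.

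**What to change.** - Reconcile the primary objective in the Trial Summary with the outcome in Section 10: say whether the primary outcome is the baseline biopsy or the pathway, and name the unit.
- For the baseline-biopsy objective, report the number newly diagnostic out of evaluable participants (at most 59) with an exact 95% CI. State that the standard rate is 0 by eligibility, and drop the 30% comparator, the McNemar test and the availability odds ratio for this objective.
- If the pathway comparison is kept, report it as a paired difference with a CI, and state which biopsies and unit the 30% describes.
- Restate precision per participant: 12.5, 11.7 and 10.2 points at 60, 70 and 80% with n = 59.
- State that 60% is the upper end of the BAP1 range in PM tumours, and either justify the 80% scenario against the 76.5% or say which other routes to diagnosis it includes.

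The cost is protocol wording. No new samples or data are needed, but the stated precision becomes less favourable.
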